Recruitment of prospective participants is detailed in the recruitment section. In all cases, once contact is made with a prospective participant, study personnel will provide a brief synopsis of the study, including study purpose, study procedures, potential risks and benefits, compensation and right to withdrawal from the study at any time without penalty. If interested in participating, study personnel will administer a brief screening form to the participant to ensure eligibility criteria are met. If ineligible, the participant will be informed of the reason for ineligibility and screening information will be retained without the participant's identifiable information (name, birthdate, etc.). If eligible, the research personnel will complete informed consent with the maternal participant. This informed consent may be completed in-person on paper, or remotely with a member of the research staff via Zoom (or similar platform) with an e-signature. Maternal participants will provide permission/consent for their infants to participate in the study, as infant-specific data, including background birth information and infant measurements, will be collected and the intervention has the potential to affect infant health. In all cases, maternal participants will sign and receive a copy (either hard copy or electronic copy) of the informed consent document. Any paper original copies will be kept and filed by research personnel. A separate addendum informed consent will be obtained to video-record AME sessions for interrater reliability. After informed consent, participants will complete baseline study measures/surveys (in-person, over phone or remote video/Zoom, or emailed survey; assessing maternal/fetal health, maternal demographics, maternal mood, reproductive history, body image concerns, experiences of discrimination, etc; see questionnaires for specifics) and be randomized to a group via computer-generated permuted block randomization stratified by pre-pregnancy BMI status (overweight: 25-29.9 or obese: ≥30). Subjects will have a 1:1 chance of being randomized to either study group, as indicated in the consent document. Study participation will be documented in the maternal participant's electronic medical record to alert providers to study participation. Study staff will meet remotely or in-person with participants in both groups weekly from 37 to 40 weeks of gestation for delivery of the assigned intervention. To maximize participant convenience and safety of all involved (given new standards/recommendations around social distancing) study "visits"/contact points will have the potential to be conducted completely remotely via a secure video call (e.g., HIPAA-compliant Zoom call with screen sharing when needed), audio phone call, or emailed survey. When/if feasible, preferred, and safe according to University research standards and current county-level guidance/restrictions, visits may also involve in-person meetings between the study participant and study staff (though the experimental condition lactation consultants will always deliver the intervention remotely). In-person visits may occur at the hospital/clinics before/after a prenatal visit or another mutually agreed upon convenient, private place. The details of study visits, according to assigned intervention are detailed below. Experimental Condition (AME): With the assistance of study staff, who will facilitate all study visits, participants randomized to AME will complete a test video call at enrollment, if possible, with the telelactation provider who are available for on-demand, one-on-one visits, 24/7) to increase familiarity with the service prior to AME instruction. Note that for subsequent study visits, if for any reason an IBCLC is not available, the study may use a substitute remotely-based IBCLC who is trained in study procedures. Participants will be taught the AME technique at the 37 week study visit after first viewing an introductory video demonstrating the technique. At the visit, study staff will initiate a 3-way meeting/connection with an available, remote International Board-Certified Lactation Consultant (IBCLC) and the study participant if the visit is remote (e.g., Zoom video call). If the study visit is inperson, study staff will initiate remote 2-way connection between themselves and study participant with a remote IBCLC via a secure video platform (e.g., Zoom). After connecting, the remote IBCLC will provide video-based expert instruction and guided feedback on AME and milk collection as the participant engages in the technique. Note that IBCLCs are trained in hand-expression as a fundamental professional skill and will receive additional training and oversight by study personnel (see intervention fidelity below). For participants whose study visits are conducted completely remotely, these meetings will occur via a secure HIPAA-compliant platform like Zoom which allows study participant, study staff, and IBCLC to see/converse with each other simultaneously. This will require that participants use their own electronic device (e.g., smart phone, laptop) for the visit. These meetings will be scheduled a convenient time for the participant, IBCLC, and study staff. When a video-based remote connection is not possible or problematic (e.g., WiFi issues), study staff will initiate a 3-way audio only phone call instead with the IBCLC and participant, and hand expression education will occur over audio to the extent possible, with subsequent referral to supplementary streaming videos demonstrating hand expression. As per our pilot study protocol, AME will continue for a maximum of 10 minutes during study visits (participants will also be advised to do AME for no longer than 10 minutes during their independent practice between study sessions). For any in-person study visits, any milk output will be collected into study-provided containers and syringes and stored for future analyses as per the protocol outlined below (disposition of antenatal milk). During remote sessions, any AME milk that is collected may be labeled as milk that may be given to the study, and frozen by the participant. This milk may then be collected and aliquoted by study staff at a later date (e.g., no contact porch pick-up of milk at participant's home by study staff members). For all AME sessions, additional breastfeeding education will be provided by the IBCLC as requested by participant and documented by study staff. Study staff will facilitate the overall visit (e.g., introductions, provision of milk collection containers). IBCLCs will reinforce/provide feedback on AME technique at each weekly study visit until delivery, with a similar format to the initial visit. Around the time of the initial 37 week visit (this may be before or after the visit, dependent on mode of AME education delivery), study staff will provide participants oral and written instructions to continue AME 1-2 times/day at home until delivery. Instructions (reinforced in weekly visits) will also contain information on milk storage, transport to the hospital if participant is storing milk at home, and use; AME contraindications; and when and how to seek assistance for any problems (please see attached: brochures in "other" documents). Please note that for participants whose visits will occur remotely, members of study staff will drop off supplies for AME (e.g., collection containers, labels, syringes, refrigerator boxes for transport of milk to hospital) before the first scheduled visit, so that participants have supplies at the time of their first session. These will be done in accordance with any county standards in-place at the time (i.e., no-contact porch drop-off deliveries, PPE worn if any in-person contact). Compliance with home practice, including AME timing, milk volume obtained, and any problems, will be assessed from after the first study visit until delivery via daily web-based survey "diaries" (if participant declines web-based diaries or there are technical problems with web-based diaries, participants may be provided written diaries to be returned to study personnel at a time/place to be arranged, e.g., no contact porch pick up). Web-based survey diaries will be administered with an automated SMS notification sent daily to the participant with up to 3 reminders through the day to complete. The responses to web-based diaries will be automatically recorded in a secure Access study database; if participant completes written diaries, their answers will be manually entered in Access database by study staff. With regard to the SMS alert system for the web-based diaries, a two-way text messaging system has been built at the University and associated hospital for this purpose (as has the survey/diary system itself); the system utilizes a server

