
STATISTICAL DESIGN AND POWER

Sample Size and Power

The total proposed enrollment of 280 women was determined considering a feasible rate of recruitment, expected effect size of the AME intervention on primary outcomes, testing of multiple hypotheses, and anticipated rate of attrition and protocol non-adherence at 2 weeks postpartum (primary outcome assessment). Our recent intervention research with normal weight and overweight/obese women demonstrates medium sized effects (standardized mean difference, d) for the AME intervention at 1-2 weeks postpartum compared to an education control in terms of higher levels of breastfeeding selfefficacy (AME: M=52.59, SD=9.92, Education: M=45.71, SD=15.71, d=0.53) and greater percentage of breast milk feeds (AME: M=89.50, SD=20.372; Education M=78.64, SD=27.303, d=0.45). Regarding exclusive breastfeeding at 1-2 weeks, rates of 0.27 have been reported among overweight/obese women.32 With a sample size of at least 210 (105 per group), we can detect with .80 power betweengroup differences in the proportions in breastfeeding exclusivity at 2 weeks postpartum as small as .172 (medium effect size of OR=2.55 using likelihood ratio chi-square statistics) at an adjusted test-wise significance level of .0167. While there is a fair amount of heterogeneity in the published effect sizes for breastfeeding support interventions among overweight and obese women and for AME specifically, our estimate lies in the range of reported effect sizes in the field. 12,32 While the examination of long-term efficacy of AME is more exploratory (Aim 2), we will be able to detect small to medium interaction effects between groups over time as small as f = .323 when using repeated measures F-tests with at least four postpartum outcome time points. Our pilot work and previous studies utilizing similar populations and recruitment sites indicate that we can conservatively anticipate combined study attrition and intervention dropout at ≈25%. To ensure 210 participants with complete follow-up to 2 weeks and no protocol deviations, we will enroll 280 women.

Statistical Methods

Preliminary Analyses: For Aims 1 and 2, detailed exploratory data analyses will first be performed, involving data description and data screening for anomalies (e.g., outliers, nonnormality, etc.). The results from this initial investigation will be used to: 1) describe

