The primary outcome variables of interest for the short-term efficacy of the AME intervention at 2 weeks postpartum (Aim 1) are 1) proportion of mothers providing 100% breast milk, 2) percentage of feedings that were breast milk, and 3) breastfeeding self-efficacy. Secondary breastfeeding outcomes for short-term efficacy include proportion of mothers with any breastfeeding, perceived milk supply, onset and days to lactogenesis II, and days to any formula and/or breastfeeding cessation. Secondary long-term efficacy outcomes (Aim 2), which will be assessed at all follow-up points until 12 months postpartum (or breastfeeding cessation/loss to follow-up), are duration of breastfeeding in days and any breastfeeding at postpartum follow-ups; the continuous and categorical type versions of breastfeeding exclusivity; and the proximal intervening outcomes (i.e., mediating variables) including the repeatedly measured breastfeeding self-efficacy and perceived milk supply.

Generalized linear mixed-effects modeling with linear contrasts will be used to examine the effect of treatment assignment (AME vs. attention control) for each repeatedly assessed outcome, with treatment group assignment as the between-subjects factor, time as the within-subjects factor, and an interaction between time and treatment group. Given the level of measurement and observed data distribution of the particular dependent variable, an appropriate error structure and link function to the linear predictors will be assumed. For example, for breastfeeding exclusivity and any breast feeding, each assessed as a binary variable, a binomial error structure will be assumed and a logit link to the predictors will be applied, while for the continuous type versions of breastfeeding exclusivity and the interval-scaled breastfeeding self-efficacy, a normal error

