distribution will be considered with an identity link to the linear predictors. Random effects for participants will also be included. Fixed and/or time-dependent covariates (e.g., pre-pregnancy BMI category [25.0-29.9; 3034.9; 35-39.9; 40+]) may be included secondarily to adjust for group imbalances or variables related to the dependent variables based on the literature or data screening results. Standard fit criteria (e.g., AIC and BIC) also will be used to identify the best-fitting repeated measures covariance structure. F-tests will test the main and interaction effects included in the model. Individual regression parameters will be estimated with confidence intervals. For each model, residual analyses will be conducted to identify sources of model misspecification, outliers, and influential observations. Sensitivity analyses will be performed to discern the impact of influential cases on modeling results. Linear contrasts will be specified in the repeated measures models to test whether the AME intervention demonstrates greater improvements in breastfeeding outcomes compared to the attention control at each time point, in particular, when conducting hypothesis testing on the primary short-term outcomes. Point and interval estimates will be obtained for each of the comparisons examined.

For event history type outcomes (e.g., breastfeeding duration, days to the onset of lactogenesis II, days to any formula) Cox proportional hazards regression methods will be applied to allow for possible censoring of the event of interest and inclusion of the fixed and time-dependent predictors. For summary outcomes (e.g., proportion of breast milk in-hospital), generalized linear modeling will be applied.

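### The primary 2-week self-efficacy contrast pre-specifies no antenatal covariate, which forgoes precision and leaves the choice of adjusted result open until data are seen

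*Combined protocol and SAP*

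**What the plan says.** Breastfeeding self-efficacy at 2 weeks is one of three primary outcomes (Analysis Strategies for Aims 1 and 2). Repeatedly assessed outcomes are modelled with "treatment group assignment as the between-subjects factor, time as the within-subjects factor, and an interaction between time and treatment group", plus participant random effects. Linear contrasts from that model "test whether the AME intervention demonstrates greater improvements in breastfeeding outcomes compared to the attention control at each time point".

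The same section allows fixed or time-dependent covariates as a secondary step, to deal with group imbalances or with variables related to the outcome, selected from the literature or from data screening. The only example is pre-pregnancy BMI category. Preliminary Analyses likewise makes covariates secondary and says their effect on the treatment estimate will be examined.

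The study-procedures text describes the pre-randomisation survey as "assessing maternal/fetal health, maternal demographics, maternal mood, reproductive history, body image concerns, experiences of discrimination, etc; see questionnaires for specifics". Breastfeeding surveys are scheduled at 2, 6 and 12 weeks and at 6 and 12 months postpartum (Data Collection and Procedures Unrelated to Intervention Delivery). Randomisation is stratified by BMI status alone.

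Sample Size and Power works "at an adjusted test-wise significance level of .0167", with 105 women per group. The pilot figures it cites are postpartum levels: "selfefficacy (AME: M=52.59, SD=9.92, Education: M=45.71, SD=15.71, d=0.53" for self-efficacy.

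**The concern.** A woman's confidence about breastfeeding varies before any milk expression takes place, and her antenatal score is likely to predict her score two weeks after birth. If so, leaving it out of the primary model keeps explainable between-woman variance in the error term.

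The plan's route to adjustment is also loose. Which covariates enter, and whether any do, can be settled after imbalances and associations have been inspected. An unadjusted result and one or more adjusted results could then be available with no prior statement of which is primary.

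The wording adds a small difficulty. Improvement implies a change from a starting value, but no starting value is named and the trial is sized on differences in postpartum level.

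**Working it through.** **Inputs from Sample Size and Power.** Alpha .0167 per test (.05/3; sidedness is not stated, two-sided assumed); 105 per group; self-efficacy 52.59 (SD 9.92) versus 45.71 (SD 15.71), d=.53; enrolment 280.

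**Assumed.** The correlation r between antenatal and 2-week self-efficacy is not in the documents; .3, .4 and .5 are used. A smaller true effect, d=.40, is used as an alternative to the pilot value.

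**The plan's own figures.**
- Pooled SD = √[(9.92² + 15.71²)/2] = 13.14. Then d = (52.59 − 45.71)/13.14 = 6.88/13.14 = .524, close to the stated .53.
- 210/(1 − .25) = 280, as stated.
- The stated .80 power is for exclusive breastfeeding. No power is given for self-efficacy, so there is no plan value to reproduce for this outcome. The exclusivity figures are a separate matter and are not used here.

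**Effect of adjustment.** With a baseline covariate of correlation r, the residual SD is multiplied by √(1 − r²).
- Detectable d at .80 power = (2.393 + .842) × √(2/105) × √(1 − r²) = .446 × √(1 − r²).
- Power comes from the noncentral t distribution with 208 degrees of freedom and noncentrality d × √(105/2) / √(1 − r²). For d=.40 and r=0 this is .40 × 7.246 = 2.90; for r=.5 it is 2.90/.866 = 3.35.
- Equivalent unadjusted total = 210/(1 − r²).

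| r | √(1 − r²) | Detectable d | Power, d=.53 | Power, d=.40 | Equivalent N |
|---|---|---|---|---|---|
| 0 | 1.000 | .446 | .922 | .686 | 210 |
| .3 | .954 | .426 | .946 | .734 | 231 |
| .4 | .917 | .409 | .961 | .773 | 250 |
| .5 | .866 | .387 | .978 | .824 | 280 |

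**Chance imbalance.** The difference between arms in a standardised baseline covariate has standard error √(2/105) = .138, so an imbalance above .2 SD in either direction has probability about .15. It would move the unadjusted 2-week difference by r × .2 × 13.14: .8 points at r=.3 and 1.3 points at r=.5, against the pilot difference of 6.88.

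**What shrinks the gain.**
- The 25% allowance combines attrition with intervention dropout, while the intent-to-treat analysis keeps women who stop the intervention but are followed. The analysed total therefore lies between 210 and 280. At 140 per group the same formula gives, for d=.40, .825 unadjusted and .864, .892 and .927 at r=.3, .4 and .5.
- If half the women had no baseline value, the variance factor at r=.4 would be roughly 1 − .5 × .16 = .92, and power at d=.40 would be about .73, not .77.

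**The case against.** The strongest reply is that the plan already provides for adjustment. Preliminary Analyses looks for group imbalances, and the covariate text permits adjustment for them and for prognostic variables. A reader might infer that chance imbalance goes uncorrected; the documents do not support that. What stands is narrower: adjustment is optional, secondary, partly data-driven, and names no antenatal feeding measure.

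A reader might also infer that antenatal self-efficacy is not measured. The baseline list is explicitly open and points to questionnaires not supplied, so the file shows only that the measure is unnamed. Nor does the model text say which time points enter. If self-efficacy is in the baseline survey, a baseline time point could fit the stated model and give the improvement wording its literal meaning. It is therefore too strong to say that improvement cannot be shown.

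A third tempting reading is that the primary test is invalid. It is not: under randomisation, chance imbalance neither biases the unadjusted contrast nor raises its type I error.

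The wording point is minor. The sentence also covers exclusivity and percentage of feeds, which have no antenatal value, and it can be read simply as better outcomes than control.

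**Conclusion.** The point holds as a matter of precision and pre-specification, not validity. The primary self-efficacy contrast could be made more precise with one covariate fixed in advance, and the plan leaves that choice until data have been seen.

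At the pilot effect the gain is modest, from .92 to about .95–.98, or roughly 2 to 6 percentage points. At d=.40 it is .69 to about .73–.82, or roughly 5 to 14 points. The smaller effect is worth considering because Sample Size and Power itself acknowledges that published effects vary.

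These figures rest on assumed correlations of .3 to .5, two-sided testing, 210 women analysed and a baseline value for nearly all of them. They concern self-efficacy only. No gain has been quantified for adjusting the two feeding outcomes for intention, and the linear-model formula does not carry over to the logit model for exclusivity.

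**What to change.** 1. Check the baseline questionnaires. If they hold an antenatal self-efficacy scale, name it in the SAP, before analysis, as a fixed covariate in the primary 2-week self-efficacy contrast. Keep the unadjusted contrast as a sensitivity analysis.
2. If they do not, add the short scale to the existing pre-randomisation survey for remaining enrolment, and handle missing baselines by imputation. Preliminary Analyses already provides for multiple imputation of predictors.
3. Replace the improvement wording with a between-group difference in level at 2 weeks, adjusted for baseline.
4. Adjusting the two feeding outcomes for intention is optional. If it is done for exclusivity, state that the adjusted odds ratio is conditional on the covariate and so is a different quantity from the unadjusted one.

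If the scale is already collected, the cost is SAP wording only. If not, it is a few minutes of survey time and missing baselines among women already enrolled, which would reduce the gain.
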